### **1.5 Dose Rationale and Risk/Benefits**

The safety and tolerance of EVP1001-1 has been evaluated in healthy volunteers, in various preclinical models and in patients with a known myocardial infarction. The doses to be tested in this study demonstrated high safety factors in animal studies and were well tolerated in human studies to date. There have been no life-threatening or other unexpected AEs. There have been no clinically meaningful changes in hematology, clinical chemistry or coagulation profile, including liver function tests. Regarding the ECG, there were no consistent drug-related changes in QT or ST segment or prolongation of the PR interval. Importantly, no cardiac depression has been observed. Results in heart patients to date were similar to those in normal volunteers with no meaningful changes in blood or urine parameters and AEs that occur at the time of dosing and resolve in less than 5 minutes whose nature is that of discomforts, transient vital sign changes.

## **2 Study Objectives**

This is a first-in-human clinical trial of combined manganese-enhanced MRI(MEMRI) and delayed-enhanced MRI(DEMRI) to determine reliable detection and clinical significance of peri-infarct injury in both the ventricles and atria. An IND approval was obtained to utilize EVP1001-1 to assess peri-infarct injury in patients with ischemic or dilated cardiomyopathy atrial fibrillation and those who undergo stem cell therapy for these indications. In preparation for a Phase I/II clinical trial, an initial safety study of 6 patients has been completed and no adverse events were observed. This proposal will enable a clinical trial of 50 patients to evaluate the safety and efficacy of MEMRI-DEMRI to characterize peri-infarct injury.

#### *Primary Objective*

Specific Aim 1 evaluates the efficacy of MEMRI-DEMRI to characterize the peri-infarct injury in the ventricles and atria.

#### *Secondary Objective*

Specific Aim 2 is a clinical follow-up to determine the occurrence of cardiovascular events.. To evaluate the safety and efficacy of MEMRI-DEMRI to characterize peri-infarct injury, in the ventricles and atria, through an innovative approach, integrating direct biological evaluation of myocardial viability and anatomical delineation of scar.

## **3 Study Design**

### **3.1 General Design**

Prior to entry into this study, all subjects will sign an Informed Consent and will then undergo a physical assessment including medical history, details regarding their cardiac history, prescription and over-the-counter drug review,, vital signs, electrocardiogram (ECG), evaluation of the major organ systems, hematology, serum chemistries. In addition, female subjects will undergo a serum pregnancy test.

Starting 30 minutes before the cardiac MRI scan (CMR), the subjects will take 16 mgs of ondansetron by mouth. CMR imaging will subsequently take place and then EVP1001-1 will then be administered approximately 15 minutes into the scan for contrast enhanced images. EVP1001-1 will be administered intravenously over approximately one minute. The subjects will each receive 0.28 mL/kg of EVP 1001-1. All subjects will be monitored closely from before ondansetron administration until their discharge from the imaging center. Following MEMRI, delayed-enhanced MRI(DEMRI)is performed using 0.2mmol/kg gadolinium. We will compare the two different contrast enhanced images (EVP1001-1 vs Gadolinium) in determining the viable, peri-infarct, and intra-infarct myocardial tissue.

To ensure a high-quality image, if the participant heart rate is greater than 65 bpm and regular rhythm, metoprolol will be given. If the HR is 65 and irregular, metoprolol will be given if there

are no contraindications (see table 1 below)

#### Beta Blocker Administration Protocol

PROTOCOL	PARAMETER(s)	ACTION(s)
Assess whether $\beta$ -blockers are necessary	If pulse is < 65 bpm and regular or if pulse is < 60 bpm and irregular  If pulse is > 65 bpm or if pulse is > 60 bpm and irregular	A $\beta$ -blocker is not given  Screen for contraindications for giving $\beta$ -blocker
Screen for contraindications for $\beta$ -blockers	If any of the following conditions exist: Heart rate, < 60 bpm Systolic blood pressure, < 100 mm Hg Decompensated cardiac failure Allergy to $\beta$ -blocker Asthma or COPD on $\beta$ 2-agonist inhaler Active bronchospasm Second- or third-degree atrioventricular block  If the above conditions are absent	A $\beta$ -blocker is not given  Oral metoprolol is given
Administer metoprolol	If giving oral metoprolol,	One 50-mg dose of metoprolol is given orally and patient is monitored over 1 hr, during which heart rate is checked every 15 min. If heart rate remains elevated, perform practice breath-hold. If heart rate still remains elevated, give IV metoprolol
	If giving IV metoprolol	Two 2.5-mg doses of metoprolol are given 5 min apart; then, two doses of 5 mg each are given 5 min apart. Total maximum dose, 15 mg. Blood pressure and heart rate are checked before each IV dose
Administer postprocedure care	If only one dose of oral metoprolol is given	No monitoring necessary, patient can leave department after study
	If IV metoprolol is given	The patient is observed for 30 min
	If heart rate drops to < 45 bpm	Consideration is given to administering atropine
	If bronchospasm occurs	A $\beta$ -agonist inhaler is given

Note—bpm = beats per minute, COPD = chronic obstructive pulmonary disease.

#### Parameters to be Measured:

A standard physical assessment will be performed on the day of imaging (approximately 1-hour post dosing). Body temperature and respiration rate will be measured within 24 hours prior to dosing and at approximately 1- and 2-hours post dose. A standard 12-lead EKG will be performed both before and after the MR study to assure no significant EKG changes have occurred. Patient's hemodynamics will also be serially monitored. A baseline BP and HR will be performed before beginning the study. After EVP1001-1 contrast infusion, BP and HR will be measured every 2 minutes until 10 minutes post EVP1001-1 contrast infusion after which point a BP and HR will be measured every 5 minutes until the conclusion of the MEMRI and every 10 minutes until the conclusion of DEMRI study. There will be a 5-minute post administration observation interval outside the scanner. The patient will also have continuous EKG monitoring during this time. After the study, the patient will have another standard 12-lead EKG performed to compare with the pre-MRI 12-lead EKG. The patient's symptoms will be

CONFIDENTIAL

This material is the property of Stanford University. Do not disclose or use except as authorized in writing by the study sponsor

reassessed 1 hour after infusion of the EVP1001-1 contrast. A differential and serum chemistry profile (with liver function test) will be performed within a month prior to administration of EVP1001-1 and within 24 hours post EVP1001-1. Adverse events (AEs) and discomforts will be recorded until discharge from the imaging center. At the 24 hour follow-up, the subject will be evaluated by telephone to determine if any AEs occurred from the time the subject left the imaging center. The subjects will have a contact number to report any AEs or to ask questions. Any clinically relevant changes from baseline in vital signs, ECG rhythm, clinical chemistries or physical condition and all AEs will be followed until resolution or until the outcome is known. Injection-associated discomforts will be recorded during administration and until imaging is completed. Primary efficacy will be based on determining whether the heart is normal or abnormal and if abnormal whether there is an infarction, ischemia or both. This provides the basis for calculating sensitivity, specificity, accuracy and predictive values. In addition, the location, size, conspicuity and associated confidence for any disease will be recorded.

The study will be stopped for any significant adverse cardiovascular event including cardiovascular death, myocardial infarction, ventricular arrhythmia, ICD firing, congestive heart failure, hospitalization, or syncope. All serious adverse events that require medical intervention and/or withdrawal of a patient will be reported to the IRB within 24 hours if it meets the unanticipated problem reporting criteria.

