
over time, offering potential benefits over the nonspecific extracellular agents currently available for MRI or X-ray/CT procedures. This feature allows full use of the high resolution of MRI, since there is not a trade-off of high spatial resolution for temporal (first-pass) resolution. It is anticipated that the features offered by EVP1001-1 along with the high resolution, three-dimensional attributes of MRI will result in higher accuracy than is available with other current modalities in practice, including stress echocardiograms, cardiac MRI using gadolinium contrast and nuclear studies such as SPECT and PET. This will be evaluated in this study and serve as the basis for pivotal registration studies. All components of EVP1001-1 are USP and are approved for use as drugs in man, orally and/or intravenously. A summary of the Phase I safety and PK (pharmacokinetics) study are provided below. The Phase I study evaluated the safety and tolerance of EVP1001-1 in humans, with special emphasis on cardiovascular safety, and assessed its PK profile. Overall, EVP1001-1 was found to be safe at all doses. There were no serious adverse events (SAE) or any events requiring medical treatment. Of special importance, no signs of cardiac depression were reported. In addition, there was no observation of prolongation of the QTc or PR intervals or other ECG-changes that had previously been reported in animals for Mn. There were no changes in hematology, serum biochemistry (including liver function tests), coagulation parameters nor in temperature, respiratory rate or blood oxygen levels. Transient increases in HR and BP were seen. These, for the most part, reflected transient changes within the normal reference range. There was no obvious dose-relationship for these responses, although their duration and magnitude were greater for the 5-minute than for the 1-minute dose administrations. Other AEs were reported, almost all which were regarded as of mild or moderate intensity. Almost all events occurred during or immediately after dosing and resolved within minutes. Over 83% of the AEs occurred during dosing and over 93% occurred within one minute of dosing. Nearly one-third of all events resolved within one minute from dosing, over 80% within 5 minutes, and 94% resolved within 1 hour. The most frequent types of AEs were injection-associated discomforts (warmth, flushing, cold, pressure, injection site changes, increased HR/BP), gastrointestinal disturbances (discomforts, nausea, vomiting, diarrhea), lacrimation and headache. Although gastrointestinal disturbances, such as nausea and occasional vomiting, resolved rapidly without treatment, these bothersome events may be avoidable through the use of a standard anti-emetic. This proved to be beneficial in humans and also in high-dose animal studies. The PK profile reflected that known for Mn in humans (based on reported radiotracer Mn studies), with a primary blood half-life under 1 minute, and less than 1% of the dose remained in the blood by 30 minutes after dosing. The performance of EVP1001-1 was as expected based on information that was in the Investigators' Brochure. Lastly, please refer to US Patent #5,980,863 regarding further details of EVP1001-1 contrast ingredients.

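### No BP/HR reading is scheduled immediately before or during the one-minute EVP1001-1 dose, and the vital-sign baseline is not tied to metoprolol, so short rises could be under-recorded or confounded

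*Combined protocol and SAP*

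**What the plan says.** The schedule is in section 3.1, under Parameters to be Measured. For the reference value: "A baseline BP and HR will be performed before beginning the study". For follow-up: "After EVP1001-1 contrast infusion, BP and HR will be measured every 2 minutes until 10 minutes post EVP1001-1 contrast infusion". Readings then come every 5 minutes to the end of MEMRI and every 10 minutes to the end of DEMRI. Continuous EKG monitoring is also promised, but the sentence points back to an unspecified period and follows the one on a 5-minute observation interval after administration.

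On timing of the dose, section 3.1 General Design says "EVP1001-1 will then be administered approximately 15 minutes into the scan for contrast enhanced images" and "EVP1001-1 will be administered intravenously over approximately one minute". Ondansetron is taken 30 minutes before the scan. Patients above a heart-rate threshold may also receive metoprolol. For the oral dose the table in 3.1 says "One 50-mg dose of metoprolol is given orally and patient is monitored over 1 hr", with heart rate checked every 15 minutes; before each IV dose, both BP and HR are checked.

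On the expected effect, section 1.1 reports from Phase I: "Transient increases in HR and BP were seen". It adds "Over 83% of the AEs occurred during dosing and over 93% occurred within one minute of dosing" and "Nearly one-third of all events resolved within one minute from dosing, over 80% within 5 minutes". Section 1.5 says that in heart patients adverse events arise at dosing, clear in less than 5 minutes, and include transient vital-sign changes.

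Section 3.2 lists vital-sign change among the key safety measures and compares pre-dose with post-dose results. It does not say which reading is the pre-dose value.

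**The concern.** The haemodynamic effect that the protocol itself names is brief and tied to the injection. The timed readings leave out the injection and the moment just before it. Two things are at stake in the section 3.2 comparison.

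- **The post-dose side.** If the first reading comes 2 minutes after the infusion ends, a rise that peaks during or just after dosing is recorded below its peak, and a very short one may not be recorded at all.
- **The pre-dose side.** The only required reference reading may be well separated from the dose. If it comes before metoprolol, the change from baseline contains the effect of a drug given to lower heart rate as well as any effect of EVP1001-1.

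There is no concurrent control group, so neither problem can be removed in the analysis. Readings not taken at dosing cannot be recovered later.

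**Working it through.** **Inputs.** Infusion about 1 minute, starting about 15 minutes into the scan (3.1). BP/HR every 2 minutes after infusion, to 10 minutes (3.1). Of all Phase I adverse events, over 83% began during dosing, nearly one-third had resolved by 1 minute and over 80% by 5 minutes (1.1; repeated in 1.4). The 83% is reported without counts, so it can be matched to the text but not recomputed.

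**Step 1: count the readings.**
- Immediately before the dose: 0 required.
- During the infusion: 0.
- In the 10 minutes after it: 5, at 2, 4, 6, 8 and 10 minutes, if the first is at 2 minutes. The text does not say whether one is also taken as the infusion ends.
- Within 5 minutes of the end of infusion: 2, at 2 and 4 minutes.

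**Step 2: share of events still present at the first reading.** From the stated figures alone, the share resolved at 2 minutes lies between about 33% and about 80%. To narrow this, interpolate between 1/3 at 1 minute and 0.80 at 5 minutes. The interpolation is an assumption.

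- Linear: R(t) = 1/3 + (0.80 − 1/3) × (t − 1)/4
- Log time: R(t) = 1/3 + (0.80 − 1/3) × ln t / ln 5

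| If resolution is timed from | t at first reading | Resolved, linear | Resolved, log time | Still present |
|---|---|---|---|---|
| End of infusion | 2 min | 45% | 53% | 47% to 55% |
| Start of infusion | 3 min | 57% | 65% | 35% to 43% |

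So roughly 35% to 55% of events would still be present at a first reading 2 minutes after the infusion. These are shares of all adverse events. No separate duration for HR/BP rises is given, so they indicate plausibility and do not estimate lost BP data.

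**Step 3: distance of the baseline from the dose.** If the baseline is taken just before the scan, it precedes the dose by about 15 minutes. If it is taken before ondansetron, the gap is about 30 + 15 = 45 minutes. If it is taken before oral metoprolol and the full hour of monitoring precedes the scan, the gap is about 60 + 15 = 75 minutes. The text allows all three.

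**Step 4: what the comparison would measure.** Observed change = EVP1001-1 effect + any metoprolol effect arising after the baseline + other drift. The documents give no size for the metoprolol term. As an assumed illustration, take a true EVP1001-1 rise of 10 bpm. If metoprolol lowers HR by 0 to 10 bpm after the baseline, the observed change runs from 10 − 0 = 10 bpm to 10 − 10 = 0 bpm. If the baseline follows metoprolol and its effect is stable, that term is zero.

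**The case against.** Several points on the other side stand.

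- The 83% is the onset of all adverse events, including discomforts, gastrointestinal events and headache. It is not the duration of HR/BP rises. An event that begins during dosing is still seen if it lasts to the next reading, and over two-thirds of events outlast one minute. A reader might infer that most rises would be missed; the figures do not show that.
- Sections 1.1 and 1.4 say that the rises were mostly within the normal range, and shorter and smaller with 1-minute than with 5-minute administration. The smaller size lowers the clinical stakes. The shorter duration makes a late first reading less informative.
- The blood half-life is under 1 minute, so under 0.5² = 25% of the end-of-infusion blood level remains at 2 minutes. It is tempting to read this as loss of the BP/HR signal. The documents never link the haemodynamic effect to blood level, so this does not help the point.
- Continuous EKG may already capture HR during the dose, and section 3.2 does not limit its comparison to the timed readings. The gap is therefore clearest for BP.
- Close monitoring and recording of events and discomforts cover dosing (3.1, 8.2). That protects the patient and captures symptoms, but it does not supply a BP value for the pre/post comparison.
- In 3.1 the word study often means the imaging exam, so the baseline may already follow metoprolol. The text does not settle this. The metoprolol checks do not close the gap: they apply only to treated patients, the checks after the oral dose are of HR only, none is required after the last IV dose, and none is named as the baseline.
- Section 14 lists a procedures flowchart that is not in the text available for review and might carry further timings.

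**Conclusion.** The point holds as a gap in measurement and definition. No BP/HR reading is required immediately before or during the dose, the analysis baseline is not named, and the EKG window is unclear. BP peaks could be under-recorded and some short rises missed. The size is unknown; the 35% to 55% range rests on interpolated figures for all events and on a first reading at 2 minutes.

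Confounding by metoprolol is conditional: it arises only if the baseline precedes the drug. A reader might conclude that the schedule is bound to produce a finding of no effect. The documents do not support that, because both the duration of the rises and the position of the baseline are left open. The change is still worth making, since the endpoint is a stated one and following the plan as written would not guarantee a usable value at the dose.

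**What to change.** In section 3.1, Parameters to be Measured:

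- Add a BP/HR reading immediately before EVP1001-1, after any metoprolol.
- Add a reading at the end of infusion and start the existing 2-minute cycle from there. Add one during the infusion if feasible.
- State that continuous EKG covers the infusion.

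In section 3.2, name the immediate pre-dose reading as the vital-sign baseline. Report peak HR from the EKG and peak BP, and keep the pre-study reading as a descriptive value. Bring the procedures flowchart into line.

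The cost is two or three extra readings per patient, matching CRF fields and a few sentences. No dose or treatment rule changes. There are downsides. A cuff may inflate during the injection, and the reported HR/BP change may be larger. A peak over several readings also tends to exceed a single baseline by chance, so show it beside the mean change at each time point.

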### **3.2 Primary Study Endpoints**

The key endpoints of this study include the assessment of safety, tolerance and efficacy of EVP1001-1. Safety and tolerance will be evaluated based on the nature and extent of AEs and injection-associated discomforts and changes in laboratory parameters, vital signs and ECG after administration of EVP1001-1. Effects, if any, of EVP1001-1 on QT/QTc intervals will be determined by comparing the intervals before and after EVP1001-1 across the full HR range for each patient, including use of individual correction of QT by RR. All subjects who receive EVP1001-1 will be included in the analyses. Pre- and post-dose results will be compared for vital signs, clinical laboratory parameters, ECG parameters and hemodynamic parameters to identify individual changes from baseline and potential systematic shifts. The presence or absence of infarcts and/or ischemic areas relative to the current clinical standard (by echo and gadolinium-based cardiac MRI) along with comparison to patient outcomes will determine efficacy.

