As for intravenous injection of any investigational drug, competent personnel and emergency facilities must be available to address severe and possibly delayed reactions after administration of EVP1001-1 or severe responses to the stress prior to EVP1001-1 administration. Subjects will be observed for AEs starting with the pre-treatment (with ondansetron), during and for at least 1 hour after EVP1001-1 administration during which time emergency equipment will be readily available. AEs will be recorded until discharge from the imaging center. At the 24-hour follow-up, the subject will be evaluated by telephone to determine if any AE occurred from the time the subject left the imaging center. In addition, the subjects will have a contact number to report any AE or to ask questions. Any clinically relevant changes from baseline in vital signs, ECG rhythm, clinical chemistries or physical condition and all AEs will be followed until resolution or until the outcome is known. AEs, if any, will be recorded on the CRF (case report form) along with the action(s) required, time of onset, duration, intensity, and outcome. A judgment will be made by the investigator as to the causality of each event. If a subject has more than one incidence of a given AE, that AE with the greatest severity will be used for analyses. If a cluster of AEs are related, a term describing the syndrome or overall adverse experience should be captured.

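### No analysis rule separates EVP1001-1 discomforts and adverse events from those after the later gadolinium injection, and the greatest-severity rule can report a recurring event at its post-gadolinium grade

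*Combined protocol and SAP*

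**What the plan says.** The order of agents is fixed. Section 3.1 states that "EVP1001-1 will then be administered approximately 15 minutes into the scan for contrast enhanced images", and then: "Following MEMRI, delayed-enhanced MRI(DEMRI)is performed using 0.2mmol/kg gadolinium". Both injections fall in one monitored session: under Parameters to be Measured, BP and HR are taken every 2 minutes for the first 10 minutes after EVP1001-1, then "every 5 minutes until the conclusion of the MEMRI and every 10 minutes until the conclusion of DEMRI study".

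The recording windows run through both injections. For discomforts: "Injection-associated discomforts will be recorded during administration and until imaging is completed". More broadly, "Adverse events (AEs) and discomforts will be recorded until discharge from the imaging center", with a telephone check at 24 hours. Section 8.2 starts the AE window earlier: "Subjects will be observed for AEs starting with the pre-treatment (with ondansetron), during and for at least 1 hour after EVP1001-1 administration".

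On the endpoint, Section 3.2 says: "Safety and tolerance will be evaluated based on the nature and extent of AEs and injection-associated discomforts", together with laboratory, vital-sign and ECG changes after EVP1001-1. It does not say when that period ends.

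On analysis, Section 8.2 provides that when a subject has a given AE more than once, "that AE with the greatest severity will be used for analyses". The same section puts onset time, duration, intensity and outcome of each AE on the CRF and asks the investigator to judge causality. Section 7 contains no safety analysis.

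**The concern.** EVP1001-1 is the investigational agent, and its tolerance is a key endpoint. Gadolinium is the reference agent, given second to every subject in the same session. If the plan is followed literally, a reaction that begins at the gadolinium injection falls inside the period that Section 3.2 uses to describe EVP1001-1. If a subject has a mild episode of some AE after EVP1001-1 and a stronger one after gadolinium, the analysed grade is the later one.

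The order is fixed and there is no arm without gadolinium, so no comparison within the trial can remove the overlap afterwards. Only timing or attribution can do it, and the plan does not say that either enters the analysis. Section 1.4 presents this study as a basis for pivotal studies, so its tolerance figures should be attributable to EVP1001-1.

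**Working it through.** The documents state no AE rate, discomfort rate or safety precision, so there is no figure to reproduce. The check is a reading of the text, followed by an illustration on assumed rates.

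**1. Do the windows overlap the gadolinium injection?** Discomforts are recorded to the end of imaging, and imaging ends with DEMRI. AEs are recorded to discharge and again at 24 hours. Both windows include the gadolinium injection.

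**2. Does anything in the analysis separate the agents?** Section 3.2 sets no cut-off at gadolinium. Section 7 is silent on safety. Section 8.2 does not list the agents against which causality is judged, and does not say that causality or onset time determines what is tabulated.

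**3. Are discomforts covered by the AE rules?** Sections 1.1 and 1.4 list injection-associated discomforts among the commonest AEs of the Phase I study; Section 3.2 and Parameters to be Measured name them beside AEs. There are two cases:
- If a discomfort is recorded as an AE, onset and causality are collected and the greatest-severity rule applies.
- If it is not, that rule does not apply, and neither onset time nor causality is specified.

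The gap differs between the two cases, but neither has an attribution rule.

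**4. Effect on frequency.** Let pE be the true rate of a discomfort or AE after EVP1001-1 and pG the rate after gadolinium. With independence and no separation, the apparent rate is 1 − (1 − pE)(1 − pG). All rates below are assumptions.

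| pE | pG | Apparent rate |
|---|---|---|
| 5% | 2% | 1 − 0.95 × 0.98 = 6.9% |
| 5% | 15% | 1 − 0.95 × 0.85 = 19.3% |
| 30% | 2% | 1 − 0.70 × 0.98 = 31.4% |
| 30% | 15% | 1 − 0.70 × 0.85 = 40.5% |

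Under independence the excess is (1 − pE) × pG, which cannot be negative. If the same subjects tend to react to both agents, the excess is smaller. It falls to zero if everyone who reacts to gadolinium has already reacted to EVP1001-1.

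**5. Effect on grade.** The severity rule matters only for subjects who have the same AE after both agents. With pE = 30%, pG = 15% and independence, that is 0.30 × 0.15 = 4.5% of subjects, or 2.25 of 50 (50 is the number in the Study Summary and Section 2; 60 and 120 appear elsewhere). If both agents share one three-grade severity distribution, the chance that the later grade is the higher is 0.223 for (0.70, 0.25, 0.05), 0.290 for (0.50, 0.40, 0.10) and 0.333 for equal thirds. That gives 2.25 × 0.223 = 0.5 to 2.25 × 0.333 = 0.75 subjects regraded. Positive association between the two reactions would raise this number while lowering the excess in step 4.

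**6. Would a split at gadolinium work?** Section 1.4 reports that over 93% of Phase I AEs occurred within one minute of dosing and over 80% resolved within 5 minutes. The BP/HR schedule implies that MEMRI normally continues beyond 10 minutes after EVP1001-1. An interval from EVP1001-1 start to gadolinium start should therefore contain most EVP1001-1 events.

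**The case against.** The strongest reply is that the plan describes recording, not pooling. Nowhere does it say that gadolinium reactions will be counted against EVP1001-1, and Section 3.2 frames the endpoint as the tolerance of EVP1001-1. That stands as far as it goes. A reader might infer that the events are pooled, but the documents support only the statement that no rule separates them.

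A reader might also infer that an EVP1001-1 episode is lost when a stronger one follows. It is not. Section 8.2 requires all AEs to be recorded, with onset, intensity and a causality judgement for each. The subject still counts as having had the event after EVP1001-1; only the analysed grade may change. Keeping the worst grade per subject is a common convention and does not itself raise the frequency.

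A third reply is that BP and HR are already collected on schedules tied to the MEMRI and DEMRI phases, which is true and makes part of the remedy free. A fourth is that any inflation overstates harm and is therefore cautious. That is fair for a safety decision. It is less helpful when the aim is to describe one agent's tolerance for later studies.

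What the reply leaves unanswered is that onset and causality are not linked to any tabulation, and are not specified at all for discomforts outside the AE record.

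**Conclusion.** The point holds as a gap in the analysis rule. The EVP1001-1 tolerance period has no end at gadolinium, the recording windows run through that injection, and the greatest-severity rule can report a recurring AE at its post-gadolinium grade. The bias in frequency is upward or nil. Its size cannot be taken from the documents: the figures above rest wholly on assumed rates, independence and no attribution by the investigator. The effect on grade is probably small unless reactions to the two agents go together.

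It would be too strong to conclude that the trial cannot describe the tolerance of EVP1001-1. For AEs the data needed are already collected; as planned, the analysis simply does not use them. The gap is firmest for discomforts that are not entered as AEs. This is a change worth making because it is cheap. It does not show that the safety results would be invalid.

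**What to change.** - Record the gadolinium start time (if the CRF, which is not included in the documents, does not already hold it) and the onset time of each discomfort.
- Tabulate AEs and discomforts by onset in four intervals: before EVP1001-1; EVP1001-1 start to gadolinium start; gadolinium start to discharge; after discharge.
- Apply the greatest-severity rule within each interval instead of across the whole session.
- Make EVP1001-1 start to gadolinium start the main tolerance window, and keep the all-interval total beside it.
- Summarise BP and HR by the existing MEMRI and DEMRI phases.
- Describe later events, and the post-session chemistry sample, as following the full sequence of agents.

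The cost is at most two CRF items and one extra table, with no added procedure or patient. The downside is that delayed EVP1001-1 events fall outside the main window, though they remain in the total.
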